1.9 Interviews, Focus Groups, or Surveys

A. Administration

Timing and Frequency

Research staff will collect interview data and drug screens from both intervention and control group subjects through video, phone interview, or in-person using standardized measures conducted at baseline and 8- and 16-weeks. Cognitive testing data will be collected at baseline and 8-weeks. If the research assessments are conducted over the phone, drug screen results will be recorded as self-reported. Additionally, subjects will engage in twice-daily EMA assessments of approximately 3-5 minutes each for 16-weeks. For 16-weeks, subjects will also initiate EMA communications to report lapses or serious cravings, which will also last for under 5 minutes. For those who do not complete their EMA, our research staff will do a timeline follow-back over the phone or video conferencing to collect missing EMA drug use data. EMA completion reports will be reviewed, weekly, and participants will be contacted, as needed, to collect missing daily drug use data.

Location

The assessments and drug screens will take place via video/online, phone interview, at their clinic, or at another safe and private location in the community (e.g., library, park, or coffee shop).

Procedures for Audio and Visual Recording

Audio or video recordings will be made of the MORE therapy sessions. All recordings will be stored in password protected computers, in a locked office at [name], or in password protected files, on the Rutgers network or HIPAA compliant Box file.

9

B. Study Instruments

Version Number: 15, 2/2/2022 Protocol Number: Pro20190016877 PI Name: [name]

Protocol Title: Mindfulness Oriented Recovery Enhancement (MORE) as an Adjunct to Methadone Treatment RESERVED FOR IRB STAMP
DO NOT MODIFY THIS SPACE

- Time until first opioid lapse assessed through ecological momentary assessment data and timeline follow-back.
- Time until MMT dropout assessed through clinic records (abstracted by the study counselor who will have access to the clinic records). Time until dropout will be calculated from enrollment until last dose of methadone.
- Total days of methadone treatment assessed through clinic records (abstracted by the study counselor who will
 have access to the clinic records). Number of days will be calculated from enrollment until each follow-up timepoint.
- Total days of opioid or any drug use assessed through EMA data and timeline follow-back

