Current substance use (Baseline, 8- and 16-- weeks). We will utilize a urine or saliva screen that tests for buprenorphine and methadone (to provide corroboration of MAT engagement and compliance) and additional substances (e.g., benzodiazepines, barbiturates, cocaine, marijuana, methamphetamine, morphine, oxycodone, phencyclidine and amphetamine). Participants will also be asked about overall number of days of use in the past 30 with questions based on PhenX Toolkit-Substance Abuse and Addictions Core Tier 1 Collection. For those prescribed opioids for pain, misuse will be assessed with the Current Opioid Misuse Measure. Drug test results conducted by the clinic during the study period will be obtained from participants' clinic charts. We will combine self-reports of opioid relapse and other drug use with biochemical measures because it is the gold standard, and without biochemical verification, self-reported drug use as an outcome variable will be questioned by the scientific community. If a biochemical measure is negative, but the participant reports drug use, the participant will be coded as using drugs since the biochemical measure will only capture a specific time point. However, if the participant self-reports drug abstinence, but the biochemical measure is positive for drug use (the more likely scenario) the participant will be coded as having used drugs.

Craving (Baseline, 8- and 16-- weeks). Opioid and other drug craving will be assessed with an adapted version of the Penn Alcohol Craving Scale (PACS)¹⁰ and the Craving Suppression Scale. The PACS is a valid, reliable, and internally consistent measure that consists of five self-report items that have been found to predict relapse. The items assess the intensity, frequency, ability to resist, and duration of craving. Originally developed to assess alcohol craving, it has been adapted and used to measure craving for various substances, including opioids,¹¹ and adapted versions have been used in trials of mindfulness-based interventions for substance use.¹² The Craving Suppression Scale is a 17 –item measure that assesses how individuals cope with craving

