Hypothesis 1.1. (**Primary Outcome**) MORE will result in longer duration of time to first opioid lapse and MMT dropout than TAU. We will use survival analysis (Kaplan Meier curves and marginal model analysis for multivariate survival data)³⁴ to test effects of MORE vs. TAU on time until first opioid lapse and MMT dropout—evidenced either on EMA, Timeline Follow-Back, urinalysis or medical records (whichever is first). Survival analysis will be run once, at 16 weeks post-baseline. Clustering within cohort will be adjusted in the multivariate marginal model analysis.³⁴ We will estimate the hazard ratios of opioid lapse and MMT dropout when comparing MORE with TAU, controlling for covariates.

Hypotheses 1.2 and 1.3 (Secondary Outcomes). MORE will result in more days of opioid abstinence (or less days of use) and a higher rate of biochemically-verified abstinence over time than TAU. Generalized linear mixed model (GLMM)³⁵ repeated measures analysis will be used. Specifically, identity link will be used for "number of abstinent days" as the dependent variable, and logit link will be used for "opioid abstinence (yes/no via urinalysis)" as the dependent variable. Days of use/abstinence will be assessed via EMA, number of drug use days since last visit and past 30 days, and the Timeline Follow-Back. In cases of conflicting findings across data sources, we will assume the highest number of days of use or lowest number of abstinent days recorded for that period. Analyses will include group (MORE vs. TAU), time, and group by time interactions as the fixed effects independent variables. Correlations among repeated measures and among subjects within cohorts will be modeled using nested random effects. Potential confounders that meet the p<0.10 criterion stated above will be entered as covariates. Linear contrasts will be constructed to test between-group differences in "days of use" or "days of abstinence" separately at each timepoint. In comparing days of use, if a substantial proportion of subjects do not use opioids, resulting in excessive zero days of use, we will use a two-part logistic/linear analysis model.^{36,37}

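### Binary opioid abstinence is coded from the test alone in section 6.1 A but from test or self-report in section 1.9 B, and one bullet in 1.9 B leaves the test out of the primary lapse

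*Combined protocol and SAP*

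**What the plan says.** **Binary abstinence.** The hypothesis in section 6.1 A is that MORE gives "a higher rate of biochemically-verified abstinence over time than TAU". The dependent variable for the logit model is then written as "opioid abstinence (yes/no via urinalysis", with no mention of self-report. The same paragraph has a rule for disagreement between sources, "In cases of conflicting findings across data sources, we will assume the highest number of days of use or lowest number of abstinent days recorded", but it is stated for day counts.

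**Coding rule.** Section 1.9 B, Current substance use, covers both kinds of disagreement. For a negative test with admitted use: "If a biochemical measure is negative, but the participant reports drug use, the participant will be coded as using drugs". The reason given is that a test sees only one point in time. For the reverse: "if the participant self-reports drug abstinence, but the biochemical measure is positive for drug use (the more likely scenario) the participant will be coded" as a user. The paragraph opens its case with "We will combine self-reports of opioid relapse and other drug use with biochemical measures because it is the gold standard".

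**Primary lapse.** The first bullet under Study Instruments in section 1.9 B reads "Time until first opioid lapse assessed through ecological momentary assessment data and timeline follow-back". Section 6.1 A, Hypothesis 1.1, takes first lapse and methadone maintenance treatment (MMT) dropout as "evidenced either on EMA, Timeline Follow-Back, urinalysis or medical records (whichever is first".

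**The concern.** A programmer who follows the abstinence definition in section 6.1 A literally will score as abstinent a participant who has told the study that he or she used opioids, provided the test on the day is negative. The coding rule in section 1.9 B says the opposite. If the choice is left open, it could be made after the data are seen.

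The lapse bullet raises the reverse problem. A participant who denies use but tests positive has no event under the bullet and has one under section 6.1 A. The protocol treats this as the commoner form of disagreement, and section 1.3 A says that inaccurate reporting is common because of social desirability. Participants know whether they attend MORE groups, so reporting could differ by arm. That makes it worth removing any doubt that the test counts.

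**Working it through.** The plan states no figure on this point, so there is nothing to reproduce. The check compares the definitions and then sizes the disagreement under stated assumptions.

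**Step 1. Cross-classify test by self-report.**

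| Drug test | Self-report | Section 1.9 B coding rule | Section 6.1 A, test alone |
|---|---|---|---|
| Positive | Use | Using | Using |
| Positive | No use | Using | Using |
| Negative | Use | **Using** | **Abstinent** |
| Negative | No use | Abstinent | Abstinent |

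The rules differ in one cell. Abstinent under 6.1 A = N(negative, use) + N(negative, no use). Abstinent under 1.9 B = N(negative, no use). The difference is N(negative, use), which cannot be below zero.

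**Step 2. How easily could an admitted user fall in that cell?** Assumptions, none from the documents: the test detects use in the last w = 2 to 4 days, and k use days fall at random in the 30 days before the visit. The 30 days match the self-report question in section 1.9 B, although the coding rule itself sets no window. The chance of a negative test is C(30−w, k) / C(30, k).

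| Use days k | w = 2 | w = 3 | w = 4 |
|---|---|---|---|
| 2 | 0.869 | 0.807 | 0.747 |
| 4 | 0.747 | 0.640 | 0.546 |
| 8 | 0.531 | 0.379 | 0.267 |

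For example, k = 2 and w = 2 gives (28 × 27) / (30 × 29) = 756 / 870 = 0.869. These figures are conditional on being an admitted user; they do not say how many participants that is.

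**Step 3. Gap as a share of all participants at a visit.** Let p be true use, s test sensitivity and r self-report sensitivity, with independent errors and no false positives. Use is classified in p·s under the test alone and in p·[1 − (1−s)(1−r)] under the combined rule. The gap is p·r·(1−s). Assumed ranges: p = 30–50%, s = 40–80%, r = 50–70%.

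- Smallest gap: 0.30 × 0.50 × 0.20 = 0.03.
- Largest gap: 0.50 × 0.70 × 0.60 = 0.21.
- Classified use runs from 12% to 40% under the test alone and from 21% to 47% under the combined rule.

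**Step 4. Sources for the primary lapse.**

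| Source | 1.9 B bullet | 1.9 B Current substance use | 6.1 A Hypothesis 1.1 |
|---|---|---|---|
| Self-report | EMA and timeline follow-back | Yes | EMA and timeline follow-back |
| Drug test | Not listed | Yes | Yes |
| Medical records | Not listed | Clinic test results are obtained from charts; their role in dating a lapse is not stated | Yes, in a list shared with MMT dropout |

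Only the bullet is out of line. None of the three places dates a lapse that is known only from a test. If it were dated at the visit, the event would fall near day 56 (8 × 7) or day 112 (16 × 7), whenever the use actually occurred.

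**The case against.** **On abstinence.** The phrase for biochemical verification can be read as self-reported abstinence confirmed by a test, with urinalysis naming only the method of confirmation. That reading is reasonable, but the dependent variable names urinalysis alone. If the broader meaning was intended, the text should say so. The rule for conflicting sources does not settle it, because it is stated for numbers of days.

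A test-only binary outcome is also defensible in itself. It is less exposed to arm-related reporting, and admitted use still enters the days-of-use outcome and counts as an event in the primary. This stands, and it is why the test-only version should be kept as a sensitivity analysis. It does not remove the contradiction with section 1.9 B.

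**On the primary outcome.** A reader might infer that section 1.9 B makes the primary lapse self-report only, and so that the primary endpoint has no settled definition. The documents do not support this. The Current substance use paragraph, in the same section, names opioid relapse and combines self-report with tests. Section 6.1 A gives an explicit rule. The bullet does not say that other sources are excluded. What remains is a bullet to be aligned.

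**On size.** A reader might also take the percentages above as bias in the treatment effect. They are not. They rest on assumed inputs and describe classification within an arm. The effect on the contrast depends on how p, s and r differ between arms, which the documents do not give.

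**Conclusion.** The conflict over binary abstinence holds. Read literally, section 6.1 A counts as abstinent a test-negative participant who admits use, against the coding rule in section 1.9 B. That its abstinence rate is equal or higher follows from the definitions and needs no assumption. The size, 3 to 21 percentage points, rests wholly on the assumed p, s and r, on independent errors and on no false positives.

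The lapse conflict is confined to one bullet in section 1.9 B, set against the rest of that section and section 6.1 A. It exposes two real gaps: whether medical records count for lapse or only for MMT dropout, and how a lapse known only from a test is dated.

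This should be fixed, but it is not critical: the primary analysis rule is already explicit, and the substantive error is in a secondary outcome.

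**What to change.** 1. In section 6.1 A, Hypotheses 1.2 and 1.3, define the logit outcome as abstinent only if the drug test is negative and no opioid use is self-reported in a fixed window before the visit, for example the past 30 days already asked about. Write urine or saliva test rather than urinalysis, since sections 1.3 A and 1.8 allow either. Keep the test-only version as a named sensitivity analysis.
2. In section 1.9 B, bring the first-lapse bullet into line with the Current substance use paragraph and with section 6.1 A.
3. In Hypothesis 1.1, separate the sources for lapse from those for MMT dropout. Say whether medical records, such as clinic drug tests, count towards lapse.
4. State how a lapse known only from a test is dated. Say also how test results that are self-reported in telephone interviews are treated in both outcomes; section 1.8 has them flagged but gives no analysis rule.

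The cost is wording; the data are already being collected. Reported abstinence rates will be equal or lower, and the binary outcome will rest partly on self-report, which the test-only sensitivity analysis helps to check.

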Data will be received by the REDCAP or Qualtrics system. Data access between the REDCap and Qualtrics databases and the web servers aew encrypted and restricted to a monitored port. All REDCap and Qualtrics data, which is displayed or captured by the user interface, is encrypted for security. Within REDCap and Qualtrics all data transactions including inserts, updates, deletions, import/export and reporting are logged. The EMA system in this study deployed via REDCap and Qualtrics will reside in a HIPAA compliant protected space. The REDCap and Qualtrics production and development servers use encrypted drives. Physical hardware will be secured in a locked facility.

The data will only be accessible to study investigators and staff. The data will be processed by an already developed REDCap or Qualtrics program that formats the data as a "long file" with one row per time point per individual participant. The investigators will employ linear mixed models to test the effects of MORE vs. the control condition on substance use, craving, pain, and other study variables. The treatment X time interaction will be the main fixed effect of interest. Models will include a random intercept, as well as a random slope if warranted by model fit statistics. Auto-correlation between repeated measures will be modeled as a first-order autoregressive function. We will also compute within-group linear mixed models examining mindfulness practice duration as a predictor of clinical outcomes.

EMA completion reports will be reviewed, weekly, and, as needed (at a maximum weekly), we will conduct a timeline follow-back⁹ with each participant to account for missing EMA drug use data. The timeline follow-back is a

10

Version Number: 15, 2/2/2022 Protocol Number: Pro20190016877 PI Name: [name]

Protocol Title: Mindfulness Oriented Recovery Enhancement (MORE) as an Adjunct to Methadone Treatment RESERVED FOR IRB STAMP DO NOT MODIFY THIS SPACE

reliable and valid measure where participants are asked to recall and record events (e.g., drug use) within a specified time period on a calendar.

Substance use history (Baseline). We will use the PhenX Toolkit-Substance Abuse and Addictions Core Tier 1 Collection⁸ to gather self-report information on lifetime use of opiates, alcohol, tobacco and substances, and past-30 day use of all substances.

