Pain (Baseline, 8- and 16-- weeks). For study eligibility, pain intensity will be assessed at baseline only with Gracely Box Scale, 13 a visual analog scale that ranges from 0 (no pain) to 20 (extremely intense pain). At baseline and both follow-up points, pain severity will also be measured with the Brief Pain Inventory (BPI; α = .87) a well-validated measure that has been widely used to tap acute and chronic pain. Participants will be asked to report their worst pain during the past week, least pain during the past week, average pain, and current pain. Response options range from 0 (no pain) to 10 (pain as bad as I can imagine). An overall pain severity score will be computed by taking the mean of the four items. Pain will also be assessed with the Sensations Body Map.

Pain interference (Baseline, 8- and 16-- weeks). Pain-related functional interference will be assessed with the pain interference subscale of the BPI⁷ (α = .88). Subjects will be asked to rate on a 0 (does not interfere) to 10 (completely interferes) scale the extent to which pain interfered with each of seven domains of normal functioning in the past week, including: general activity, mood, walking ability, normal work, relations with other people, sleep and enjoyment of life. An overall pain interference score will be computed by taking the mean of the seven items.

Coping with pain (Baseline, 8- and 16-- weeks). Cognitive coping with pain by reinterpreting painful sensations as innocuous sensory experiences will be assessed via the reinterpreting pain sensations subscale of the Coping Strategies Questionnaire¹⁴ (CSQ). This subscale has good internal consistency (α = 0.88) and is comprised of 6 items including "I don't think of it as pain but rather as a dull or warm feeling," and "I just think of it as another sensation such as numbness." Participants will be asked to report how much they generally engaged in this form of coping when they felt pain. Responses are rated on a scale ranging from 0 (never) to 6 (always); a reinterpretation of pain sensations total score can be obtained by adding up the four items (range: from 0 to 36). Scores on this scale are

Version Number: 15, 2/2/2022 Protocol Number: Pro20190016877

PI Name: [name]

Protocol Title: Mindfulness Oriented Recovery Enhancement (MORE) as an Adjunct to Methadone Treatment RESERVED FOR IRB STAMP DO NOT MODIFY THIS SPACE

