6.0 Research Data Protection and Reporting

6.1 Data Management and Confidentiality

A. Describe the data analysis plan, including any statistical procedures.

Data Analyses. Analyses will be conducted on an intent-to-treat basis. Adjustment for multiple comparisons using Bonferroni-Holm procedure²⁸ will be applied in outcome analyses. We will first examine baseline between-group differences on demographic and other key variables - those that show a difference of p<.10 will be entered as covariates in the analyses below. Given that this RCT occurs within a naturalistic treatment context (i.e. MMT programs in which study participants will also be receiving usual care), significant group differences in usual treatment (e.g., methadone dose or number of TAU psychotherapy sessions) will be treated as covariates. For all analyses specified below, we will perform sensitivity analyses to test response differences or clustering by site, group cohort, and therapist either as fixed or random effects and assess the robustness of results when accounting for these site and therapist effects. To handle **missing data**, we will conduct a series of sensitivity analyses using pattern-mixture (PM) approaches, ²⁹⁻³¹ assuming missing-at-random (MAR), ³² not-missing-at-random (nMAR) and/or a mix of nMAR and MAR, to assess plausible treatment effects in the presence of missing data. Other PM approaches such as control-based pattern imputation approach or the tipping-point approach will also be considered. ³³ The missing data handling strategy will be carefully selected depending on the distributions, type, and mechanism of missing data (informative vs. non-informative).

Version Number: 15, 2/2/2022 Protocol Number: Pro20190016877 PI Name: [name]

Protocol Title: Mindfulness Oriented Recovery Enhancement (MORE) as an Adjunct to Methadone Treatment RESERVED FOR IRB STAMP
DO NOT MODIFY THIS SPACE

AIM 1 Analyses.

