Hypotheses 1.4 (**Secondary Outcomes**). MORE will result in more days of MMT and greater decreases in pain severity, pain interference, days of non-opioid drug use, and emotional distress over time than TAU. We will use GLMM to compare days of MMT, pain severity and interference scores, days of non-opioid drug use, and emotional distress among the treatment groups, using the same analytic strategy described above.³⁵

AIM 2 Analyses. Mediational analysis. To test whether the three mediators specified in Aim 2 statistically mediate the effect of treatment on changes in days of opioid use over time, we will conduct a multivariate path analysis via a latent growth curve framework conducted in structural equation modeling software (i.e., MPlus) according to established guidelines³⁸ evaluating 3 regression paths for each mediator: A) 'a' path between treatment indicator and pre-post treatment change in the mediator (e.g., savoring); B) the 'b' path between pre-post treatment change in the mediator (e.g., savoring) and the latent slope (change) of the outcome (e.g., opioid use); and C) the 'c' path between treatment indicator and the latent slope of the outcome (e.g., opioid use). We will emulate similar multivariate analyses from published studies of meditation interventions^{39,40} by testing treatment effects on the latent slope of changes in days of drug use over time as mediated by changes in proposed mechanisms. We will test mediation by evaluating the significance of the joint product of the a and b paths, with bootstrapping used to test the significance of the indirect effect. A similar model will be estimated for changes in pain severity. Path models will be corrected for multiple comparisons. Simultaneous estimation of mediational effects from all three mediators to days of drug use and pain will allow us to determine unique effects of the core therapeutic mechanisms of MORE (mindfulness, reappraisal, savoring) – representing one of the most comprehensive mediation modeling attempts of the MORE intervention research program to date.

Version Number: 15, 2/2/2022 Protocol Number: Pro20190016877 PI Name: [name]

Protocol Title: Mindfulness Oriented Recovery Enhancement (MORE) as an Adjunct to Methadone Treatment RESERVED FOR IRB STAMP
DO NOT MODIFY THIS SPACE

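### Adjustment for the outcome's own baseline value is not pre-specified for the pain and distress outcomes, which gives up precision

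*Combined protocol and SAP*

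**What the plan says.** Section 6.1 A, Hypotheses 1.2 and 1.3, sets out a generalized linear mixed model for repeated measures: "Analyses will include group (MORE vs. TAU), time, and group by time interactions as the fixed effects independent variables". It continues: "Linear contrasts will be constructed to test between-group differences in" days of use or days of abstinence, one timepoint at a time. Hypothesis 1.4 extends this to pain severity, pain interference, emotional distress, non-opioid drug use and days of methadone treatment, "using the same analytic strategy described above".

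Covariates are chosen by a baseline test. Among demographic and other key variables, "those that show a difference of p<.10 will be entered as covariates in the analyses below". The mixed-model paragraph repeats the rule: "Potential confounders that meet the p<0.10 criterion stated above will be entered as covariates".

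Section 1.9 B, in the text on momentary assessment, describes linear mixed models for substance use, craving, pain and other variables, and says: "The treatment X time interaction will be the main fixed effect of interest".

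Baseline values exist for the continuous outcomes. Section 1.9 B says: "At baseline and both follow-up points, pain severity will also be measured with the Brief Pain Inventory". It schedules pain interference at the same three visits, and depression and anxiety scales at every research visit.

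No section names the outcome's own baseline value as a planned covariate, or gives the arms a common baseline mean. No section says whether the baseline visit is one of the response rows.

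**The concern.** Randomisation makes the expected baseline means equal in the two arms. A model that uses this fact, or that conditions on each participant's baseline score, estimates the same treatment effect with a smaller standard error and removes chance baseline differences. The planned model does neither by design.

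The stakes are the power and stability of the pain and distress comparisons. No sample size or power is stated for them, and they also carry a Bonferroni-Holm correction. In addition, the per-timepoint contrast and the group-by-time test can point in different directions when the arms differ by chance at baseline, and Section 6.1 A does not say which of them decides Hypothesis 1.4.

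**Working it through.** **Plan's own figure.** There is none for these outcomes. The only stated size, 47 per group, is for time to opioid lapse. It matches Freedman's formula for a hazard ratio of 0.55 (94 events, 94/2 = 47, if every participant has an event) and has no bearing on this point.

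**Inputs.**
- 92 per arm (Section 1.5; 184/2). Section 6.1 B prints 85 per group beside the same total of 184.
- Two-sided alpha 5% and power 80%, borrowed from the primary calculation: 1.960 + 0.842 = 2.80.
- Baseline-to-follow-up correlation r: not in the documents; assumed 0.3 to 0.7.
- Equal SD at all visits, complete data, no cohort clustering: assumed.

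**Formulas.** The variance of each between-arm contrast, in units of 2·SD²/n, is:
- raw follow-up difference: 1
- change from baseline (group-by-time): 2(1-r)
- adjusted for own baseline, or common baseline mean: 1-r²

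For any r strictly between 0 and 1, 1-r² is below 1. It is also below 2(1-r), because the ratio of the two is (1+r)/2, which is less than 1.

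**Detectable effect.** Raw: 2.80 × √(2/92) = 0.413 SD. The others multiply this by the square root of the relative variance.

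| r | Variance: raw / change / adjusted | Detectable SD: raw / change / adjusted |
|---|---|---|
| 0.3 | 1.00 / 1.40 / 0.91 | 0.41 / 0.49 / 0.39 |
| 0.5 | 1.00 / 1.00 / 0.75 | 0.41 / 0.41 / 0.36 |
| 0.6 | 1.00 / 0.80 / 0.64 | 0.41 / 0.37 / 0.33 |
| 0.7 | 1.00 / 0.60 / 0.51 | 0.41 / 0.32 / 0.295 |

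At r=0.5 the gain over either unadjusted contrast equals 1/0.75 = 1.33, or 33% more participants.

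**If baseline is a response row.** One complete data set was simulated with 92 per arm, r=0.5 and no true effect. The week-16 contrast from the group, time and group-by-time mixed model was -0.127 (SE 0.150), identical to the raw mean difference. The week-16 interaction was +0.076 (SE 0.145). The common-baseline estimate was -0.018 (SE 0.127). The first two differ in sign because the arms differed by chance at baseline by -0.127 - 0.076 = -0.203.

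**If baseline is not a response row.** It is unused unless the p<.10 rule admits it.

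**Does the p<.10 rule repair this?** In 20,000 simulated trials with a true effect of 0.413 SD, assuming that the baseline score counts as a key variable, the rule adjusted in about 10% of trials.

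| r | Power: unadjusted / p<.10 rule / always adjusted | Type I error under the rule |
|---|---|---|
| 0.5 | 79% / 81% / 89% | 4.0% |
| 0.7 | 80% / 83% / 97.5% | 3.1% |

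The rule recovers little of the lost power and is conservative.

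**The case against.** The planned model is a standard and valid repeated-measures analysis. Several defences have force.

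- **The plan does have an adjustment rule.** If a baseline outcome score counts as a key variable, which the text allows but does not confirm, the p<.10 rule would adjust for the largest imbalances. A reader might infer that baseline is never used. The documents support only that its use is not pre-specified.
- **The interaction may be the intended test.** Hypothesis 1.4 speaks of greater decreases, Section 1.9 B favours treatment by time, and the sentence on per-timepoint contrasts names only days of use or abstinence. A group-by-time test that includes the baseline visit uses baseline by subtraction. The fair comparator for pain and distress may therefore be the change contrast, against which the gain is smaller at high r: 0.37 to 0.33 SD at r=0.6, and 0.32 to 0.295 at r=0.7. It remains a gain for every r below 1.
- **Separate arm means at baseline are an inference.** Section 6.1 A does not list the response visits. The conclusion does not depend on this, because neither reading pre-specifies adjustment.
- **The figures are idealised.** The 92 per arm is a recruitment ceiling that already allows for attrition. With missing follow-up data the mixed model borrows some information from baseline. Clustering by group cohort is left out.

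None of these supplies the missing pre-specification.

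**Conclusion.** The point holds for BPI pain severity, BPI pain interference, depression and anxiety (the last two taken here as the measures of emotional distress). For these the plan does not pre-specify adjustment for the outcome's own baseline value, and pre-specifying it would improve precision. The size depends on an r that the documents do not give. The saving against the raw contrast is 9% of variance at r=0.3, 25% at r=0.5 and 49% at r=0.7. Against the change contrast it is 35%, 25% and 15%.

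Three stronger readings are not supported:

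- **That the planned tests are biased or inflate type I error.** Under randomisation they are valid, and the p<.10 rule makes them slightly conservative.
- **That the main result of the trial is affected.** The primary outcome is a survival analysis and does not use this model.
- **That every secondary outcome loses precision in this way.** Days of methadone treatment are counted from enrollment and have no baseline. Drug-use days since the last visit have no stated like-for-like baseline. For the logit-link abstinence outcome, adjustment changes the conditional odds ratio, so the variance formulas do not apply.

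**What to change.** In Section 6.1 A, Hypotheses 1.2 to 1.4, for the continuous outcomes with a baseline measure, pre-specify one of two models, regardless of the baseline p-value:

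1. weeks 8 and 16 as the responses, with the outcome's own baseline value as a fixed covariate for every participant; or
2. all three visits as responses, with the arms constrained to a common baseline mean.

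Name the adjusted week-8 and week-16 contrasts as the tests for these outcomes, and state which visits are response rows. State also which baseline is used when the survey is repeated because more than 3 months passed before the group started (Section 1.3 A). For drug-use days, baseline past-30-day use may serve as the covariate. Leave days of methadone treatment out. If abstinence is adjusted, say that the odds ratio is conditional on baseline.

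The cost is a few sentences of analysis-plan wording and the definition of baseline. No new data are needed.
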